5.6.1 Extent of Exposure

The duration of treatment will be calculated as the number of days between the date the subject receives the 1st treatment dose and the date the subject receives the last dose of treatment. These values will be used to summarize the extent of exposure to study drug.

5.6.2 Adverse Events

The AE verbatim descriptions (investigator terms from the CRF) will be classified into standardized medical terminology using the Medical Dictionary for Regulatory Activities (MedDRA). AEs will be coded to the MedDRA (Version 23 or higher) lower level term closest to the verbatim term. The linked MedDRA PT and primary system organ class (SOC) are also captured in the database.

A TEAE is defined as an AE that emerges during treatment up to the subject's last dose or up to 28 days after the subject's last dose for subjects who do not enter the extension phase (for core study analysis) or do not enter Study E2023-A001-405 (for extension phase analysis), having been absent at pretreatment (Baseline) or

- Reemerges during treatment, having been present at pretreatment (Baseline) but stopped before treatment, or
- Worsens in severity during treatment relative to the pretreatment state, when the AE is continuous.

Only those AEs that are treatment-emergent will be included in summary tables. All AEs, treatment-emergent or otherwise, will be presented in subject data listings.

The TEAEs will be summarized by treatment group. The incidence of TEAEs will be reported as the number (percentage) of subjects with TEAEs by SOC and PT. A subject will be counted only once within an SOC and PT, even if the subject experienced more than 1 TEAE within a specific SOC and PT. The number (percentage) of subjects with TEAEs will also be summarized by maximum severity (mild, moderate, or severe).

Eisai Final 4.0 Confidential Page 18 of 30

The number (percentage) of subjects with TEAEs will also be summarized by relationship to study drug (Yes [related] and No [not related]).

The number (percentage) of subjects with treatment-related TEAEs will be summarized by SOC and PT. Treatment-related TEAEs include those events considered by the investigator to be related to study treatment. The number (percentage) of subjects with treatment-related TEAEs will also be summarized by maximum severity (mild, moderate, or severe).

The number (percentage) of subjects with TEAEs leading to death will be summarized by MedDRA SOC and PT. A subject data listing of all AEs leading to death will be provided.

The number (percentage) of subjects with treatment-emergent SAEs will be summarized by MedDRA SOC and PT for each treatment group. A subject data listing of all SAEs will be provided.

The number (percentage) of subjects with TEAEs leading to discontinuation from study drug will be summarized by MedDRA SOC and PT for each treatment group. A subject data listing of all AEs leading to discontinuation from study drug will be provided.

The number (percentage) of subjects with TEAEs leading to treatment dose adjustment will be summarized by MedDRA SOC and PT. A subject data listing of all AEs leading to treatment dose adjustment will be provided.

Adverse events will be summarized by the following subgroups: age (≥ 2 to <12 yrs, ≥ 12 yrs), sex (male, female), and race (white, black, other).

5.6.3 Laboratory Values

Laboratory results will be summarized using Système International (SI) units, as appropriate. For all quantitative parameters listed in protocol Section 9.5.1.4.4. Safety Assessments (Laboratory Measurements), the actual value and the change from baseline to each postbaseline visit and to the end of treatment (defined as the last on-treatment value) will be summarized by visit and treatment group using descriptive statistics. Qualitative parameters listed in protocol Section 9.5.1.4.4 will be summarized using frequencies (number and percentage of subjects), and changes from baseline to each postbaseline visit and to end of treatment will be reported using shift tables. Percentages will be based on the number of subjects with both nonmissing baseline and relevant postbaseline results.

Laboratory test results will be assigned a low/normal/high (LNH) classification according to whether the value was below (L), within (N), or above (H) the laboratory parameter's reference range. Within-treatment comparisons for each laboratory parameter will be based on 3-by-3 tables (shift tables) that compare the baseline LNH classification to the LNH classification at each postbaseline visit and at the end of treatment. Similar shift tables will be used to compare the baseline LNH classification to the LNH classification for the highest and lowest value during the treatment period.

Eisai Final 4.0 Confidential Page 19 of 30

The Sponsor's Grading for Laboratory Values (see Section 13, Appendix 13.1) presents the criteria that will be used to identify subjects with treatment-emergent markedly abnormal laboratory values (TEMAVs). Except for phosphate, a TEMAV is defined as a postbaseline value with an increase from baseline to a grade of 2 or higher. For phosphate, a TEMAV is defined as a postbaseline value with an increase from baseline to a grade of 3 or higher. When displaying the incidence of TEMAVs, each subject will be counted once in the laboratory parameter high and in the laboratory parameter low categories, as applicable. Incidence of Hy's law will be summarized.

5.6.4 Vital Signs

Descriptive statistics for vital signs parameters (diastolic and systolic blood pressure, pulse, respiration rate, temperature, weight and changes from baseline) will be presented by visit and treatment group.

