7 INTRODUCTION

7.1 Compound Overview

Lorcaserin hydrochloride is a selective serotonin 5-hydroxytryptamine (5-HT)_{2C} receptor agonist that is being developed for treatment of Dravet syndrome. Lorcaserin hydrochloride selectively mimics the effects of 5-HT at the 5-HT_{2C} receptor and was designed to activate 5-HT_{2C} receptors without significant agonism of the 5-HT 2A (5-HT_{2A}) or 5-HT 2B (5-HT_{2B}) receptors at therapeutic doses. Functional assays indicate that lorcaserin selectivity for the human 5-HT_{2C} receptor is approximately 14- and 61-fold relative to the human 5-HT_{2A} and 5-HT_{2B} receptors, respectively, and showed little or no appreciable interaction with other 5-HT receptors, the 5-HT transporter, or a panel of additional receptors and ion channels.

Lorcaserin was approved by the US FDA on 27 Jun 2012 as an adjunct to a reduced calorie diet and increased physical activity for chronic weight management in adults.

During the review of a postmarketing required 12,000 patient cardiovascular outcome trial, the primary safety analysis showed no meaningful difference between lorcaserin and placebo in risk of major adverse cardiovascular events, demonstrating noninferiority (Bohula et al., 2018). An assessment of malignancies in this study showed a small numerical imbalance (0.6%) in the lorcaserin arm with 462 (7.7%) lorcaserin-treated subjects diagnosed with 520 primary cancers and 423 (7.1%) placebo-treated subjects diagnosed with 470 cancers (based on an FDA analysis). While the data did not support a finding of causation with respect to such cancers, the FDA determined that this numerical imbalance in malignancies nonetheless resulted in an unfavourable benefit:risk for the weight management

indication and on 11 Feb 2020, the FDA requested that Eisai voluntarily withdraw BELVIQ® from the market.

After the public announcement of the BELVIQ withdrawal, direct requests were made to Eisai and FDA by physicians, caregivers, and advocacy groups regarding the future availability of lorcaserin for the treatment of refractory epilepsies, such as Dravet syndrome. After consultation with the FDA, Eisai has made lorcaserin available via an Extended Access Program for refractory epilepsies to patients who were prescribed BELVIQ before the market withdrawal announcement and, based on their treating physician judgment, continue to derive clinical benefit.

For more details refer to the Global Investigator Brochure.

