7.2 Clinical Experience

Tolete et. al (2018) summarize a retrospective chart review (Jan 2014 – Jan 2018) of 36 patients with childhood-onset refractory epilepsies (Dravet syndrome [20 patients], Lennox-Gastaut syndrome [9 patients], other treatment-resistant focal epilepsies [3 patients], and generalized epilepsies [3 patients]) administered lorcaserin. Thirty-three (94.3%) patients were taking at least 1 antiseizure medication (mean = 3; clobazam [60%], valproic acid [57.1%], and cannabidiol [40%]). Of the 35 patients analyzed, the median percentage reduction from baseline in the mean monthly frequency of motor seizures was 47.7% ($z=-3.04$, $P<0.01$; 46.9% in tonic-clonic, 62.3% in tonic, 60.1% in atonic, and 54.6% in focal seizures with motor features); 15 (42%) had greater than 50% reduction in motor seizures. Two (5.7%) patients had increased seizure frequency. The mean lorcaserin dosage was 15.7 mg/d (and 13.7 mg/d for children) and median treatment duration was 10.8 months. After 15 months, 50% of patients remained on lorcaserin. The most common AEs reported were decreased appetite (19.6%), decreased attentiveness (17.1%), and weight loss (11.1%). The mean decline in body mass index (BMI) at last follow-up compared to baseline was $-0.58 \pm 0.24 \text{ kg/m}^2$ ($-2.7 \pm 1.3\%$; $P=0.02$) and was similar among patients taking or not taking valproate. Five patients stopped treatment before 30 days due to side effects. The above nonclinical and clinical information on lorcaserin justifies the development of lorcaserin in Dravet.

The study design and duration of treatment was selected based on Guidelines for Industry on Clinical Evaluation of Antiepileptic Drugs (FDA, 1997) and is similar to the design of registration clinical studies of Epidiolex, drug approved for treatment of Dravet syndrome (Devinsky et al., 2017) and recently reported fenfluramine study in Dravet syndrome (Lagae et al., 2020). Sample size was estimated based on the percent reduction of convulsive seizures and standard deviation reported in fenfluramine study in Dravet syndrome (Lagae et al., 2020).

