9.3.1 Inclusion Criteria

Subjects must meet all of the following criteria to be included in this study:

1. Male or female, age ≥ 2 years at the time of informed consent (or assent)
2. Confirmed diagnosis of epilepsy with Dravet syndrome per Recommendations from a North American Consensus Panel (2017)
3. Has had at least 4 convulsive seizures during the 4 weeks of the Prerandomization Phase
4. Currently treated with at least 1 AED and the doses of all AEDs must be stable for at least 4 weeks before Screening, and be expected to remain stable throughout the study.
5. If vagal nerve stimulator, responsive neurostimulator, or deep brain stimulator is used, it must be implanted at least 5 months before Screening, parameters must be stable for at least 4 weeks before Screening, and be expected to remain stable throughout the study
6. If a ketogenic diet is followed, it must be stable for at least 4 weeks before Screening and be expected to remain stable throughout the study

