9.5.1.1 Screening Assessments

9.5.1.1.1 DEMOGRAPHY

Subject demography information will be collected at the Screening Visit. Demography information includes date of birth, sex, race/ethnicity.

Height and weight will be measured at the Screening Visit.

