5.6 Safety Analyses

Safety analyses will be conducted on the Safety Analysis Set. The data will be summarized by overall, treatment group, using descriptive statistics (eg, n, mean, standard deviation, median, minimum, maximum for continuous variables; n [percentage] for categorical variables).

The incidence of TEAEs, SAEs, AEs leading to discontinuation of study drug, and AEs leading to dose adjustment will be summarized. The incidence of TEAEs will be summarized by severity (mild, moderate, or severe), as well as by relationship to treatment (related or not

Eisai Final 4.0 Confidential Page 17 of 30

related). Proportion of subjects with increased seizure frequency, weight and BMI changes will be summarized.

The change from baseline in vital signs and ECG parameters will be summarized, and changes from baseline in laboratory values will be summarized for continuous variables.

Incidence of FDA-defined valvulopathy, pulmonary hypertension, and change from baseline of echocardiographic parameters will be summarized. Incidence of bradycardia, new onset heart block, new onset of other arrhythmias or conduction abnormalities, thickened valve leaflets, and restricted valve leaflet motion will be summarized.

Proportion of subjects with any treatment-emergent study-specific AEs will be summarized.

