5.9 Extension Phase Analyses

Efficacy Analyses

Descriptive statistics will be provided for the efficacy endpoints in the Extension Phase. Mean, standard deviation, median, minimum, and maximum will be provided for continuous endpoints and number and percentage will provide for categorical variables. In addition, plots will be used to summarize the data. Efficacy analyses will be performed similarly to the Core Study analyses and all analyses will be on the treatment duration (Core Study and Extension Phase).

Safety Analyses

All safety analyses will be performed on the Safety Analysis Set. Safety data that will be evaluated include monitoring and recording all adverse events; regular laboratory evaluation for hematology, blood chemistry, and urinalysis; periodic measurement of vital signs, weight and ECGs; and the performance of physical and neurological examinations. Safety analyses will be performed similarly to the Core Study analyses and all analyses will be on the treatment duration (Core Study and Extension Phase).

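### Weight and BMI changes are not standardised for age and sex and height is taken only at Screening, so within-arm changes in growing children, chiefly in the uncontrolled Extension, can understate drug-related weight loss

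*SAP*

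**What the plan says.** SAP 5.6.4 summarises vital signs descriptively; "pulse, respiration rate, temperature, weight and changes from baseline) will be presented by visit and treatment group". Protocol 9.7.1.8.4 says the same, and protocol 9.5.1.4.5 records weight in kg. SAP 5.6 and protocol 9.7.1.8 add one further output: "Proportion of subjects with increased seizure frequency, weight and BMI changes will be summarized". It has no cut-off and no direction. Neither document plans a z-score, a percentile or any other measure standardised for age and sex.

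The eligible population is "Male or female, age ≥ 2 years at the time of informed consent (or assent", with no upper age limit. On height, protocol 9.5.1.1.1 says "Height and weight will be measured at the Screening Visit". Protocol Table 3 marks height at Visit 1 only, and Table 4 (Extension) has no height row. Weight is taken at every treatment visit in both tables.

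The protocol itself gives the reason to watch weight. Section 7.1 describes the earlier approval as an "adjunct to a reduced calorie diet and increased physical activity for chronic weight management in adults". Section 7.2 reports, from the epilepsy chart review, "The most common AEs reported were decreased appetite (19.6%), decreased attentiveness (17.1%), and weight loss (11.1"%), and a mean BMI decline of 2.7%.

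For the Extension, in which everyone receives lorcaserin, SAP 5.9 states: "Safety analyses will be performed similarly to the Core Study analyses and all analyses will be on the treatment duration (Core Study and Extension Phase"). SAP 8.2 sets the safety baseline as the last assessment before randomization and gives no separate Extension baseline.

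**The concern.** A child who should be gaining weight and does not has lost ground, but a table of change in kg shows zero or a small gain. BMI would normally help. Here, with one height per subject, percent change in BMI is simply percent change in weight.

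The Extension is where this matters most. There is no concurrent control to show what growth alone would have done, and the period runs to Week 26, so more growth accumulates. Former-placebo subjects are a special case. Measured from the pre-randomization baseline, their Week 26 change includes 14 weeks of growth before any lorcaserin, and the SAP does not say how they are grouped.

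The age split does little to help. Protocol 9.7.1.8 promises safety data by age group, but SAP 5.6 omits this and SAP 5.6.2 keeps it for adverse events only, in two bands (2 to under 12, and 12 and over).

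At stake is how an Extension weight table is read. A mean gain in kg could be taken as reassurance when it does not separate growth from a drug effect.

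**Working it through.** The plan states no figure on this point, so there is none to reproduce. The check is whether ordinary growth is of the same size as a plausible drug effect.

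**Inputs**
- From the documents: 14-week Core and 12-week Extension, hence 26 weeks; weight bands starting at 10, 20 and 40 kg; BMI decline of 2.7% (protocol 7.2). When height is fixed, percent change in BMI equals percent change in weight, so 2.7% is used as a size for weight loss. In the chart review it was seen at last follow-up, with median treatment of 10.8 months. Applying all of it by Week 14 is an assumption.
- Assumed, not in the documents: normal gain of 1.5 to 4 kg/year; height gain of 5 to 8 cm/year from 110 cm.

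**Growth against loss**

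Gain = rate × weeks/52. Loss = 0.027 × weight. Net raw change = gain − loss.

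For 20 kg and 2 kg/year:
- Loss = 0.027 × 20 = 0.54 kg.
- 14 weeks: gain = 2 × 14/52 = 0.54 kg; net about 0.
- 26 weeks: gain = 2 × 26/52 = 1.00 kg; net +0.46 kg.

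Across the assumed range:

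| Weight | 2.7% loss | Net at 14 weeks (1.5 to 4 kg/year) | Net at 26 weeks (1.5 to 4 kg/year) |
|---|---|---|---|
| 10 kg | 0.27 kg | +0.13 to +0.81 kg | +0.48 to +1.73 kg |
| 20 kg | 0.54 kg | −0.14 to +0.54 kg | +0.21 to +1.46 kg |
| 40 kg | 1.08 kg | −0.68 to 0.00 kg | −0.33 to +0.92 kg |

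Masking is therefore plausible and is greatest in small children and at Week 26. It is not universal: a 40 kg subject growing slowly still shows a loss, and an adult's weight change contains no growth.

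**Former-placebo subjects**

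Of the 1.00 kg expected over 26 weeks in the 20 kg child, 0.54 kg falls in the placebo period and 2 × 12/52 = 0.46 kg in the Extension. More than half of the growth in the Week 26 change comes before any exposure.

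**BMI with a stale height**

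For a child of 110 cm with flat weight, BMI change using the Screening height is 0%. With updated height it is (h0/h1)² − 1.
- 5 cm/year: −2.4% at 14 weeks (h1 = 111.35 cm) and −4.4% at 26 weeks (h1 = 112.5 cm).
- 8 cm/year: −3.8% at 14 weeks (h1 = 112.15 cm) and −6.9% at 26 weeks (h1 = 114 cm).

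The planned BMI summary shows none of this.

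**Core comparison**

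Both arms grow, so growth largely cancels in lorcaserin minus placebo. I simulated 40,000 trials of 11 per arm (22 randomized, SAP 7). All inputs are assumed: ages uniform from 2 to 18; 12 kg at age 2, then +2 kg/year to age 10, +4 to 15 and +1.5 to 18; a true 2.7% loss; 2% measurement noise. The mean Week 14 difference was −0.84 kg. It was negative in 99.4% to 99.7% of trials at 0.75 to 1.5 times that growth, and in 98.0% to 99.5% after adding 50% between-subject variation in growth. The Core comparison works.

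**The case against.** The case against is substantial, and most of it stands.

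- **The Core has a control.** The weight table is by treatment group and, as computed above, the difference shows the effect despite growth. Randomization is not stratified by age, but it is stratified by weight and balanced by a Pocock-Simon method (SAP 3.2). That limits chance imbalance in the variable that most directly drives change in kg.
- **Kg tables are not the only output.** There is the proportion summary in SAP 5.6, and weight loss or decreased appetite reported as adverse events is tabulated by preferred term, severity and relationship, and by age and sex (SAP 5.6.2).
- **The proposed measure has its own bias.** These children have severe epilepsy, take at least one antiepileptic drug and may follow a ketogenic diet, so they may grow slowly for reasons unrelated to lorcaserin. On the simulated growth curve above, with true growth at 0.75 times the reference, 50% between-subject variation and no drug effect, the reference-adjusted mean at Week 26 was a loss in 89% of groups of 11.
- **The trial is small and terminated**, and the table shells, which may include a percent-change display, are in a separate document.

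A reader might infer that weight is summarised only in kg, that growth hides weight loss throughout the trial, or that a known harm will be reported as absent. The first three points rule these out. Nor should one argue that a growth-adjusted mean would always reveal a true loss: a simulation that subtracts the same growth curve that generated its data shows this by construction.

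What the objection does not answer is the within-arm reading of the Extension. An adverse event term depends on someone reporting it, and a child who gains less than expected need not prompt one. The proportion has no threshold, and BMI adds nothing without repeated height.

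**Conclusion.** The point holds in limited form. Without age and sex standardisation, and with a single height per subject, raw within-arm change in weight or BMI cannot separate growth from drug effect in growing children. This bites chiefly in the uncontrolled Extension out to Week 26. In the worked example of a 20 kg child gaining 2 kg/year, growth cancels a 2.7% loss at 14 weeks and leaves an apparent gain of 0.46 kg at 26 weeks. The size rests on assumed growth rates and on a BMI decline borrowed from an uncontrolled chart review; neither is an estimate for this trial.

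In the Core the placebo comparison largely shows the effect. The documents do not support the claim that weight harm would go unreported. This is an inexpensive improvement to a safety table, and it matters more because SAP 7 reduces efficacy to descriptive statistics while leaving the safety summaries in place.

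**What to change.** In SAP 5.6.4 and 5.9:

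- Keep the kg table.
- Add change from baseline in weight-for-age-and-sex z-score, by visit and treatment group, for the ages covered by the CDC growth reference that protocol 9.4.4 already cites. For older subjects, add percent change in weight.
- In the Extension, show former-placebo subjects separately, with their own z-score change over the Core placebo period alongside as context.
- State that Extension z-score changes are descriptive and not proof of drug harm, because a general-population reference may show slow disease-related growth as a decline.

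The cost is a few lines of text, one derived variable and one or two tables. Date of birth, sex and weight are already collected (protocol 9.5.1.1.1 and 9.5.1.4.5), so no new visit or measurement is needed. A BMI z-score would need repeated height, which the schedule does not provide, and is not proposed here.

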5.6.5 Electrocardiograms

ECG assessments will be performed at Unscheduled visit, if needed. Descriptive statistics for ECG parameters and changes from baseline will be presented by visit and treatment group. Proportion of subjects with New FDA-defined valvulopathy will be summarized by visit and treatment group.

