9.3.3 Removal of Subjects From Therapy or Assessment

The investigator may withdraw the subject from the study at any time for safety or administrative reasons. The subject may stop study drug or withdraw from the study at any time for any reason.

The reason for discontinuation will be documented. If a subject discontinues study treatment, the subject will enter the Follow-Up Period and complete protocol-specified off-treatment visits and procedures. The investigator should confirm whether a subject will withdraw from study treatment but agree to continue protocol-specified, off-treatment study visits, procedures, or whether the subject will withdraw from the study. If a subject or guardian/legally authorized representative withdraws consent (or assent), the date will be documented in the source documents.

A subject who discontinues study treatment should be followed for subsequent protocol-specified visits and procedures. If a subject discontinues study drug but remains in the study, the set of end-of-treatment procedures, Early Treatment Discontinuation according to Early Discontinuation Visit schedule, will be administered, and further information will be collected at visits according to regular Schedule of Procedures/Assessments. The primary reason for discontinuation and all other reasons contributing to the subject’s discontinuation from study drug will be collected. If a subject discontinues from study treatment and the study at the same time, Early Discontinuation Visit will be conducted followed by safety Follow-up Visit (see [Section 9.5.5](#)).

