4 DETERMINATION OF SAMPLE SIZE

A sample size of 54 subjects (27 per group) will have 90% power to detect a difference of 50% reduction in convulsive seizure frequency per 28 days between lorcaserin and placebo assuming a standard deviation of 55, using a 2-group t-test with 0.05 two sided significance level. This sample size will have 90% power to detect an odds-ratio of at least 10 for the secondary endpoint 50% reduction in convulsive seizure frequency, assuming the placebo response is 12%, using a 2-group Chi-square test with 0.05 two-sided significance level. Sample size was estimated based on the percent reduction of convulsive seizures and standard deviation reported in fenfluramine study in Dravet syndrome (Lagae et al., 2020). Approximately 62 subjects will be randomized assuming a dropout rate of 12%.

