8.3 Definition of Visit Windows

Table 3 of the protocol presents the schedule of procedures/Assessments. The screening/baseline period is four weeks long and procedures/assessments are performed at randomization, weeks 1, 2, 4, 6, 10, and 14 of the treatment period with a follow-up of 4 weeks after end of treatment. Table 3 presents the protocol specified visits/weeks and corresponding time windows used for visit-wise analyses are presented in terms of days relative to the randomization. If more than one measurement is included in a visit window, the measurement collected closest to the scheduled date will be used in the analysis. In the case where two measurements were collected an equal number of days before and after the Scheduled Day the later of the two measurements will be used for analysis. For ECHO assessments when assessing a new or worsened event then the most severe assessment will be selected if 2 or more assessments fall within a visit window

Eisai Final 4.0 Confidential Page 23 of 30

Table 3 Visit Windows Measurements

Scheduled	Scheduled Week	Scheduled	Time Window (Days)	
1	Screening		First day of Screening	-1
2	Baseline/ Randomization	1	1	
3	1	7	2	10
4	2	14	11	17
5	4	28	18	34
6	6	42	35	48
7	10	70	49	82
8	14	98	83	101
Extension Phase				
9	15	105	102	110
10	17	119	111	125
11	20	140	126	149
12	23	161	150	169
13	26	182	170	194

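### An ECG or echocardiogram taken at early discontinuation before Day 83 misses the Week 14 row of the by-visit tables, and SAP 5.6.5 has no end-of-treatment row to hold it

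*SAP*

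**What the plan says.** - **Schedule.** Protocol Table 3 places post-baseline Core Study ECGs and echocardiograms at Visit 8 (Week 14) and at the ED visit. Unscheduled tests are possible if needed. Vital signs and weight are taken at every treatment visit and at ED.
- **Summaries.** SAP 5.6.5 on ECG: "Descriptive statistics for ECG parameters and changes from baseline will be presented by visit and treatment group". On the valve endpoint: "Proportion of subjects with New FDA-defined valvulopathy will be summarized by visit and treatment group". SAP 5.6.4 uses the same rule for vital signs and weight: "weight and changes from baseline) will be presented by visit and treatment group".
- **Visit assignment.** SAP 8.3: "corresponding time windows used for visit-wise analyses are presented in terms of days relative to the randomization". The window table there has no ED row, no end-of-treatment row and no condition that the subject is still on drug.
- **Laboratory tests.** SAP 5.6.3 goes further and summarises "the actual value and the change from baseline to each postbaseline visit and to the end of treatment (defined as the last on-treatment value").
- **After stopping drug.** Protocol 9.3.3 says that, for a subject who stops drug but remains in the study, "further information will be collected at visits according to regular Schedule of Procedures/Assessments". Another sentence in that section sends a subject who stops treatment into the Follow-Up Period.
- **Termination.** SAP 7 cuts back the efficacy and PK analyses after 22 randomizations. It does not change the safety tables.

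**The concern.** For ECG and echocardiogram, Week 14 is the only Core Study row after baseline in which every continuing subject is due a reading. A subject who stops early has one substitute, the ED reading. The day windows decide where it goes. Before Day 83 it goes to a row that holds only the occasional ED or unscheduled test, so it appears there with an n of perhaps one and contributes nothing to the summary that readers will use. The Week 14 row then leaves out some of the subjects who stopped early, including any who stopped for tolerability.

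There is a second, less certain route. If a subject stays in the study off drug, the Week 14 reading taken off drug enters the Week 14 row of the randomized arm with no mark to show it.

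At stake is who is represented in the ECG parameter table (QTc included) and in the by-visit proportion with new valvulopathy. With 22 subjects randomized, one or two misplaced readings are a visible share of an arm.

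**Working it through.** **1. The plan's own figures.** SAP 4 needs 54 evaluable subjects and allows 12% dropout: 54 / (1 − 0.12) = 61.4, rounded up to 62, as stated. SAP 7 reports 22 randomized: 22 / 62 = 35.5%, given there as 35%.

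**2. Where an ED reading goes.** The windows in SAP 8.3, over Days 2 to 97 (after randomization and before the scheduled Week 14 day), are:

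| Row | Window (days) | Days counted | ECG or echo scheduled? |
|---|---|---|---|
| Week 1 | 2–10 | 9 | No |
| Week 2 | 11–17 | 7 | No |
| Week 4 | 18–34 | 17 | No |
| Week 6 | 35–48 | 14 | No |
| Week 10 | 49–82 | 34 | No |
| Week 14 | 83–101 | 15 (Days 83–97) | Yes |

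Days that map to a row before Week 14: 9 + 7 + 17 + 14 + 34 = 81 of 96, or 84%. Days that map to Week 14: 15 of 96, or 16%. An ED test on Day 40 is filed under Week 6, one on Day 82 under Week 10, and one on Day 83 under Week 14.

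**3. How many subjects.** Expected early stoppers at 12%: 0.12 × 62 = 7.4 and 0.12 × 22 = 2.6. The documents give no stopping times. If these are uniform over Days 2 to 97 (assumption), the number with an ED reading before Day 83 is 7.44 × 81/96 = 6.3 of 62, or 2.64 × 81/96 = 2.2 of 22. With the 7% dropout rate in Protocol 9.7.2, the figure for 22 subjects is 0.07 × 22 × 81/96 = 1.3.

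The range over other timing patterns is wide. If half of the stoppers leave before Day 83, the numbers are 3.7 of 62 and 1.3 of 22. If all do, they are 7.4 and 2.6. If none do, they are zero.

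**4. The off-drug route.** Visit 8 is due on Day 98 ± 3, that is Days 95 to 101, which lies wholly inside the Week 14 window. An off-drug Visit 8 reading therefore always enters that row. If an ED ECG on Day 85 and an off-drug ECG on Day 98 both exist, their distances from the scheduled day are 13 and 0 days, so the closest-reading rule in SAP 8.3 keeps the off-drug one. For new or worsened echocardiographic events SAP 8.3 keeps the worse reading, but only among readings in the same window. An ED echocardiogram on Day 60 stays in the Week 10 row.

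**5. Vital signs and weight.** These are measured at all of Weeks 1, 2, 4, 6, 10 and 14. An ED value falls in a populated row near its true exposure time, so it is not stranded.

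**The case against.** The strongest case on the other side has five parts.

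- **The by-visit tables are not the only summaries.** SAP 5.6 also plans, with no visit rule, the incidence of FDA-defined valvulopathy, pulmonary hypertension, bradycardia, heart block and other arrhythmias, and the proportion with weight and BMI changes. A reader might infer that an ED reading is lost to the report. It is not: it still appears in an earlier row and may count in these incidences. What remains is that SAP 5.6 does not say which readings count. It also mentions change in ECG parameters in general terms, but only 5.6.5 says how that change is tabulated.
- **Adverse event reporting catches marked findings.** Protocol 9.5.1.4.1 treats a QTcF above 460 ms with a rise of more than 60 ms as an AE. Protocol 9.5.1.4.3 makes new or worsened valvular disease, pulmonary hypertension and new arrhythmia always serious. This stands and lowers the stakes. It does not replace a summary of the parameters.
- **The off-drug route is uncertain.** Protocol 9.3.3 contains sentences that point both ways, and the Follow-up column of Protocol Table 3 has no vital signs, ECG or echocardiogram. The sentences must be reconciled. The loss of ED readings from Week 14 does not depend on them.
- **The laboratory rule is not a full remedy.** SAP 5.6.3 adds a row but does not restrict its by-visit rows to on-drug values. This stands. It also argues against moving off-drug readings to listings only, which could take a late valvulopathy out of the by-visit table.
- **Other documents may settle it.** SAP 9 and 11 defer derivation rules and table shells to documents not available here. An end-of-treatment row may exist there, but the SAP does not call for one.

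**Conclusion.** The point holds for the ECG parameter table and for the by-visit proportion with new FDA-defined valvulopathy. An ED ECG or echocardiogram before Day 83 is filed where neither test is scheduled and is absent from the Week 14 row. For vital signs and weight the missing row is only a matter of consistency with the laboratory section.

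The size is about 7 of 62 or 2 to 3 of 22 subjects stopping early, of whom about 6 or 2 would have an ED reading outside Week 14. This rests on two things: the 12% is a planning allowance for reaching the Full Analysis Set target, not an estimate of how many subjects have an ED test, and the 84% assumes uniform stopping times.

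Two stronger readings are tempting and are not supported. A reader might infer that ED readings never reach Week 14, but those on Days 83 to 101 do. A reader might also infer that the tables understate the drug's cardiac effect. The documents do not say how stoppers' readings differ from completers', and if a change grows with exposure, an early ED reading would show less of it. Direction and size of any bias are unknown.

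This is a cheap improvement to descriptive safety tables and affects no planned test.

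**What to change.** 1. In SAP 5.6.5, and for echocardiographic parameters in 5.6, add the end-of-treatment summary that 5.6.3 already defines as the last on-treatment value. State that the ED reading fills this row for subjects who stop early.
2. Report the proportion with new FDA-defined valvulopathy at end of treatment as well as by visit.
3. Keep off-drug readings in the by-visit rows but flag them, and keep them in the overall valvulopathy incidence.
4. Reconcile the sentences of Protocol 9.3.3 on what follows when study drug is stopped, so that it is clear whether off-drug Week 14 readings will exist.
5. Optionally add the same row to SAP 5.6.4 for consistency.

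The cost is a SAP wording change and one extra row per table, from data already collected. The downside is that the new row mixes different lengths of exposure, as the laboratory tables already do.
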